8.2.2 RELATIONSHIP TO STUDY AGENT

The study investigator will assess the relationship of any serious adverse event or adverse events that lead to discontinuation of study medication to be related or unrelated by determining if there is a reasonable possibility that the reported event may have been caused by the treatment. To ensure consistency of AE/SAE causality assessments, study investigators should apply the following general guideline when determining whether an AE/SAE is related:

• **Related:** There is a plausible temporal relationship between the onset of the event and administration of the study treatment, and the event cannot be readily explained by the participant's clinical state, intercurrent illness, or concomitant therapies; and/or the event follows a known pattern

- of response to the study treatment; and/or the event abates or resolves upon discontinuation of the study treatment or dose reduction and, if applicable, reappears upon re-challenge.
- Not related: Evidence exists that the event has an etiology other than the study treatment (e.g., preexisting medical condition, underlying disease, intercurrent illness, or concomitant medication); and/or the event has no plausible temporal relationship to study treatment administration (e.g., cancer diagnosed 2 days after first dose of study drug); and/or an alternate etiology has been established.

If necessary, the PCC PI or investigator will consult with CC in order to determine the relatedness of an AE/SAE.

8.2.3 EXPECTEDNESS

The PCC PIs will be responsible for determining whether of any serious adverse event or adverse events that lead to discontinuation of study medication is expected or unexpected. An AE/SAE will be considered unexpected if the nature, severity, or frequency of the event is not consistent with the risk information previously described for the study agent in the package insert. If necessary, the PCC PI or investigator will consult with CC in order to determine the expectedness of an AE/SAE.

8.3 TIME PERIOD AND FREQUENCY FOR EVENT ASSESSMENT AND FOLLOW-UP

Serious adverse events (SAEs) occurring during the study period must be recorded. SAEs that are related to the study medication that are still ongoing at the end of the study period must be followed up to determine the final outcome. SAEs that occur within 30 days after study drug discontinuation will occur within the period of long-term follow-up as specified by the protocol. SAEs will be reported on a SAE form in the EDC system (see MOP).

8.4 REPORTING PROCEDURES

8.4.1 ADVERSE EVENT REPORTING

Each PCC PI is responsible for adhering to the oversight and safety reporting requirements of their center's Institutional Review Board or the central IRB.

8.4.2 SERIOUS ADVERSE EVENT REPORTING

Unexpected, related serious events must be reported to the CC immediately after the event comes to PCC staff attention via completion of the EDC SAE form. If the study participant required hospitalization, the hospital discharge summary must also be sent to the CC. In the event of problems with the online SAE form, the PCC PI or investigator will contact the CC. CC staff will report these events to the applicable regulatory authorities within the required timelines (see MOP for details).

Unexpected, related SAEs are reviewed by the Medical Monitor to verify the coding and the reporting that is required. These and all other reported SAEs are reviewed by the DSMC. MedDRA coding conventions will be used. The CC will notify all PCC PIs of the DSMC findings and recommendations.

8.4.3 UNEXPECTED/UNANTICIPATED PROBLEM REPORTING

Incidents or events that meet the OHRP criteria for unexpected/ unanticipated problems require the notification of the CC. It is the site investigator's responsibility to report unexpected/ unanticipated problems s to their IRB and to the CC.

To satisfy the requirement for prompt reporting, unexpected/ unanticipated problems will be reported using the following timeline:

- unexpected/unanticipated problems that are SAEs will be reported to the CC within 24 hours of the investigator becoming aware of the event.
- It is the PCC PI's responsibility to notify institutional officials and/or the IRB of unexpected/ unanticipated problems that are SAEs, as required.

8.4.4 EVENTS OF SPECIAL INTEREST

Not applicable.

8.4.5 REPORTING OF PREGNANCY

Women of child bearing will have a pregnancy test prior to enrollment, if it is positive they will be ineligible for the study. If a study participant thinks she may be pregnant the study staff will request that she immediately stop the study medication and have a pregnancy test. If the pregnancy test is positive the study medication will be stopped permanently; the study participant will be referred to see her doctor and will continue to be followed by the study staff. The study investigator will notify their PCC PI who will notify their IRB and the CC within seven (7) days. The CC will notify the DSMC and FDA within fifteen (15) days.

The study investigator will have permission to follow the pregnant study participant to determine pregnancy outcome.

8.5 STUDY HALTING RULES

A formal interim analysis is proposed and is described in the SAP. In addition, a continuous sequential safety stopping rule is planned to monitor the study based on unexpected events. In this study, the predominant safety concern is acute kidney failure. The DSMC may recommend halting the study for safety, efficacy or other reasons (SAP).

8.6 SAFETY OVERSIGHT

A DSMC has been appointed by the National Eye Institute (NEI) to monitor safety unmasked to treatment at regular intervals (at least once/6months).

Safety oversight will be under the direction of the DSMC that is composed of individuals with the appropriate expertise, including ophthalmology, statistics, clinical trials and ethics. The DSMC will meet at least semiannually to assess safety and efficacy data on each group of the study. The DMSC will operate under the

rules of an approved charter that outlines the operating guidelines for the committee and the procedures for the interim evaluations of study data and will be written and reviewed at the organizational meeting of the DSMC. At this time, each data element that the DSMC needs to assess will be clearly defined. The DSMC will provide advice to NEI. The DSMC will monitor study participant safety and review performance of the trial. Reports will be prepared regularly in accordance with the plan outlined in the charter and as requested by the DSMC chair, and will include interim analysis(es) of primary and secondary endpoints; additional safety events; and other information as requested by the committee. After each meeting, the DSMC will give advice to the NEI about the continuation of the study. After approval by the NEI, a summary of the DSMC report and recommendations will be forwarded by the CC to investigators for submission to their local and central IRBs, as applicable. DSMC reports will be the primary mechanism for reporting safety concerns to NEI and IRBs.

Sequential safety procedures (54) for life-threatening conditions in clinical trials will be employed. The unmasked study statisticians will be responsible for the oversight and implementation of this plan. Results will be provided to the DSMC.

If study participant safety requires unmasking, such as in the event of overdose of study medication, unmasking will be available through a 24-hour helpline answered by a physician medical monitor. Procedures for this unmasking and for its documentation are described in the MOP.

9 CLINICAL MONITORING

PCC monitoring is conducted to ensure that the rights and well-being of human subjects are protected, that the reported trial data are accurate, complete, and verifiable, and that the conduct of the trial is in compliance with the currently approved protocol/amendment(s), with GCP, and with applicable regulatory requirement(s). Monitoring for this study will be performed by ZEDS CC staff.

The CC is the first line of contact for trial PCC staff and investigators regarding current protocol and CRF versions, forms, procedures, quality, monitoring, and other study components, ensuring PCC understanding and operationalization of the protocol, and successful identification of eligible patients for screening and enrollment, protocol adherence and study participant retention. Substantial written correspondence and logs of phone conversations will be filed within the ZEDS mailbox. All IRB related correspondence will be filed in the PCC's file within the ZEDS Trial Master File (TMF).

Study recruitment, enrollment, and retention are monitored based on reports generated by the data acquisition and management system. Study screening information is reviewed by comparing the characteristics of study participants enrolled versus screened out, assisting with potential strategies to improve study enrollment. The ratio of screened to randomized participants is also reviewed. Enrollment and visit attendance is also monitored on an ongoing basis by participant, by PCC, and for the overall study.

Data performance indicators for each PCC and for the overall study are also reviewed. These include CRF-level and field-level completeness, data accuracy, data entry timeliness, query resolution timeliness. Essential protocol adherence requirements are also monitored from the database. Important components of adherence monitoring include ensuring that informed consents are signed and dated by the participant, confirming that study participants are re-consented in accordance with protocol specifications (if needed), and making sure that inclusion and exclusion criteria are met. PCCs with study participants who have excessive missed study visits, as well as data collected outside the permitted visit windows are identified, and participants who are not

adhering to protocol medication or treatment compliance requirements are identified and reported to the appropriate study personnel.

A crucial part of data integrity monitoring is the ongoing review, monitoring and cleaning of study data for completeness and accuracy. During this process CC staff reviews trends in data collection patterns across centers. Issues are flagged as they arise and resolved accordingly. The data management staff will communicate these trends and data collection issues to NEI and study monitors at the CC to ensure that monitors are aware of the issues and can appropriately review and verify PCC data.

This trial will utilize centralized, remote, and risk-based monitoring for regulatory, data and safety monitoring, along with onsite monitoring for specified source verification and risk management, for cause. Initially the PCCs have been required to provide information related to the training of the study investigator, coinvestigators and coordinators, and past research experience. The centers have also been assessed to determine the extent at which they have access to electronic medical records (EMR) and to electronic data capture (EDC). If additional centers are added similar information will be obtained.

The CC will ensure the training of monitoring personnel prior to initiation of study enrollment and as specified in MOP to ensure the monitoring plan is executed. This will include but not be limited to training of monitors on specific protocol requirements, monitoring plans, and standard operating procedures.

Details of PCC monitoring are documented in a Clinical Monitoring Plan (CMP). The CMP describes in detail who will conduct the monitoring, frequency of monitoring will be done, at what level of detail monitoring will be performed, and the distribution of monitoring reports.

10 STATISTICAL CONSIDERATIONS

10.1 STATISTICAL ANALYSIS PLAN

A Statistical Analysis Plan provides a complete description of all statistical considerations and analysis plans (see SAP).

10.2 STATISTICAL HYPOTHESES

The primary objective of this randomized controlled clinical trial is to test the hypothesis that long-term suppressive antiviral treatment for 1 year with oral valacyclovir 1000 mg daily delays the time to the first occurrence of new or worsening anterior segment ocular disease (*dendriform epithelial keratitis*, *stromal keratitis*, *endothelial keratitis*, *and/or iritis*) compared to placebo by 12 months.

The secondary objectives are (1) a) to test the hypothesis that long-term suppressive antiviral treatment for 1 year with oral valacyclovir 1000 mg daily delays the time to the first occurrence of new or worsening anterior segment ocular disease (*dendriform epithelial keratitis, stromal keratitis, endothelial keratitis, and/or iritis*) compared to placebo by 18 months; and b) to test the hypothesis that the occurrence of new or worsening disease in the 6 months post treatment period is reduced for participants treated with valacyclovir compared to placebo; and (2) to test the hypothesis that suppressive treatment for 12 months with oral valacyclovir 1000 mg daily reduces the

incidence, severity and duration of post herpetic neuralgia (PHN) compared to placebo at 12 and 18 months in patients with HZO.

To evaluate these hypotheses, the following endpoints will be evaluated:

Primary Efficacy Endpoint:

The primary endpoint is the time to first occurrence of new or worsening episode of dendriform epithelial keratitis, stromal keratitis, endothelial keratitis, and/or iritis due to HZO, accompanied by pre-specified changes in treatment for the same disease manifestation of HZO (see MOP) during the twelve months of treatment. The primary endpoint is compared for participants randomized to study medication or placebo.

To assess the primary objectives, study participants will be monitored at each visit for new or worsening any of the following conditions (see MOP for definitions):

- 1. Dendriform epithelial keratitis:
- 2. Stromal keratitis
 - a. Without ulceration
 - b. With ulceration
- 3. Endothelial keratitis
- 4. Iritis

The endpoint of first occurrence of new or worsening dendriform epithelial keratitis, stromal keratitis, endothelial keratitis, and/or iritis will be determined by clinical examination accompanied by prespecified changes in treatment (see MOP), as there are no validated confirmatory biomarkers or other tests.

Secondary Efficacy Endpoints:

To assess the secondary objectives, the study participants will be monitored at each visit for the following:

- Time to development and number of episodes of new or worsening dendriform epithelial keratitis, stromal keratitis, endothelial keratitis, and/or iritis due to HZO, requiring pre-specified changes in treatment (see MOP), during the 18 months following randomization, that includes the 6 months following cessation of treatment; and during the 6 months following the end of the 12 month treatment period.
- 2. The incidence, severity, and duration of PHN at one year of treatment, and after the 6 month post-treatment follow up.
- 3. Impact of vaccination against zoster with RZV on outcomes.
- 4. Development of specific manifestations of HZO, classified as dendriform epithelial keratitis, stromal keratitis (all types), endothelial keratitis, iritis requiring pre-specified changes in treatment (see MOP), neurotrophic keratopathy with or without melting and/or microbial superinfection, episcleritis, and/or scleritis during the twelve months of treatment.
- 5. Secondary glaucoma as determined by IOP and treatment required.

Exploratory Efficacy Endpoints:

- 1. Changes in strength and/or frequency of prescribed topical corticosteroids at 12 and 18 months.
- 2. Occurrence of stroke
- 3. Occurrence of temporal arteritis/giant cell arteritis
- 4. Occurrence of myocardial infarction

- 5. Occurrence of new or worsening malignancy
 - a. Solid tumor (other than non-melanoma skin cancer)
 - b. Hematologic malignancy
 - c. Lymphoma.
- 6. Time to development and number of episodes of new or worsening dendriform epithelial keratitis, stromal keratitis, endothelial keratitis, and/or iritis due to HZO, with a recent substantial reduction in treatment (see MOP) during 12 months of treatment.
- 7. Impact of suppressive antiviral treatment prior to enrollment on outcomes during 12 months of study treatment.

10.3 ANALYSIS DATASETS

All study participants who were randomized into the study will comprise the intent-to-treat population, the primary analysis population for efficacy. Study participants who received at least one dose of the assigned study drug will comprise the as-treated population, the primary analysis population for safety. Note, participants on either arm can receive off study valacyclovir or other antivirals after the primary endpoint is reached or for the occurrence of herpes simplex. During the time period that other antivirals are received, participants must be off study medication. Therefore, safety analyses will be conducted in this as-treated population until participants go off treatment at the end of the study or receive off treatment antiviral therapy for a primary endpoint or for herpes simplex. For this subset of participants who receive antiviral therapy for these reasons, additional analyses of safety for the time period following resumption of study medication will be conducted. Further supportive analyses of safety will be carried out for study participants who complete 12 months of treatment. Details provided in SAP.

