If the study participant develops a possible primary endpoint - new or worsening dendriform epithelial keratitis, stromal keratitis, endothelial keratitis, and/or iritis - and the study investigator thinks the study participant may benefit from a one to two-week course of open label oral antiviral treatment, the study medication will be temporarily discontinued, and resumed when the course of open label treatment is completed. (After a study participant develops a possible primary endpoint, if topical antiviral treatment is prescribed, the study medication is continued.)

Permanent Discontinuation due to Prolonged Open Label Use of Valacyclovir, Acyclovir or Famciclovir for HZO

If the study participant develops a possible primary endpoint - new or worsening dendriform epithelial keratitis, stromal keratitis, endothelial keratitis, and/or iritis - and the study investigator thinks the participant may benefit from prolonged open label antiviral treatment, the study medication will be discontinued, and the participant will continue to be followed. Any open label use of antivirals will be collected and centrally monitored.

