10.4.5 SAFETY ANALYSES

All study participants who were randomized into the study will comprise the intent-to-treat population, the primary analysis population for efficacy. Study participants who received at least one dose of the assigned study drug will comprise the as-treated population, the primary analysis dataset for safety.

The analysis datasets for safety are described in Section 10.3 (Analysis Datasets) above. Details are provided in SAP.

The occurrence of acute kidney failure, defined as requiring temporary or permanent dialysis, in these patients will be monitored using a safety monitoring rule as described in the SAP and compared between the two treatment groups.

SAEs will be analyzed in a similar manner. For all safety events, the rates of study drug termination will be summarized and compared by treatment group and strata.

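### Section 10.3 defines only on-treatment safety windows, so serious adverse events during open-label antivirals, or after them without resumption, enter no stated comparison by arm

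*Combined protocol and SAP*

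**What the plan says.** Section 10.3 sets the safety population: "Study participants who received at least one dose of the assigned study drug will comprise the as-treated population, the primary analysis population for safety". It then limits the time that counts: "safety analyses will be conducted in this as-treated population until participants go off treatment at the end of the study or receive off treatment antiviral" treatment, where the reason for the antiviral is a primary endpoint or herpes simplex. The rationale given is that nobody takes study drug while on another antiviral.

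Two further analyses are named. For those who received such antivirals, "additional analyses of safety for the time period following resumption of study medication will be conducted". In addition, "Further supportive analyses of safety will be carried out for study participants who complete 12 months of treatment". Section 10.4.5 points back to these datasets: acute kidney failure requiring dialysis "in these patients will be monitored using a safety monitoring rule as described in the SAP and compared between the two treatment groups", and SAEs are to be handled likewise.

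Collection is wider than analysis. Section 8.3 says "Serious adverse events (SAEs) occurring during the study period must be recorded", and Table 1 schedules SAE assessment at every visit from month 3 to month 18. Section 6.1.8 covers participants with a possible primary endpoint for whom the investigator judges that "the participant may benefit from prolonged open label antiviral treatment, the study medication will be discontinued, and the participant will continue to be followed". Sections 10.3 and 10.4.5 leave details to the SAP, whose text is not in the document supplied.

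**The concern.** Under section 7.6, open-label oral antivirals for zoster eye disease are barred until a possible primary outcome. The antiviral cut is therefore a post-randomization event linked to outcome, and it should occur more often on placebo if the drug works. Efficacy is analysed by intent to treat, with endpoints at 12 and 18 months. Harm is analysed over windows that can close earlier, so benefit and harm would not describe the same follow-up.

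The events at stake include the one that section 8.5 calls the predominant safety concern. A participant who needs dialysis during an open-label course, or months after moving to prolonged open-label treatment, would be recorded as having an SAE but would have no stated place in the comparison of the arms.

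**Working it through.** **Coverage.** Recorded SAE time set against the analyses named in section 10.3:

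| Period | Stated analysis |
|---|---|
| On study drug, before any open-label antiviral | Main analysis |
| During an open-label course for a primary endpoint or herpes simplex | None |
| After study drug is resumed | Separate additional analysis |
| After prolonged open-label use, no resumption (6.1.8) | None |
| Early stop for intolerance, eGFR or pregnancy, no open-label antiviral | Not listed as a cut-off |
| Months 12-18 | None if the cut-off is month 12; main analysis if it is month 18 |

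The time window of the completer analysis is not given. It cannot reach participants who left study drug for prolonged open-label treatment before month 12. Study drug stops at the 12-month visit (7.3.3), whereas section 7.6 gives the study's duration as 18 months, so the cut-off phrase in 10.3 fits either date.

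**Design figures (10.5).** 390 per arm, 12-month failure 30% versus 21.3%, hazard ratio 0.67, 80% power, two-sided 0.05.
- Hazard ratio: ln(0.787)/ln(0.70) = 0.672.
- Expected endpoints: 390 × 0.30 = 117 and 390 × 0.213 = 83, together 200.
- Power: 79.6% by two proportions, 80.4% by Schoenfeld's formula with 200 events.

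The stated figures reproduce.

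**Person-time removed in year 1.** Assumptions: constant hazard, no dropout, and a share q of endpoint participants who receive open-label antivirals and do not resume. The documents do not give q, so a range is used.
- Hazards per year: placebo -ln(0.70) = 0.3567; valacyclovir -ln(0.787) = 0.2395.
- Mean time to endpoint, truncated at one year, (1 - e^-h)/h: 0.30/0.3567 = 0.841 and 0.213/0.2395 = 0.889 years.
- Person-years removed per arm: 390 × q × (1 - mean time).
- Total planned follow-up: 780 × 1.5 = 1,170 person-years.

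| q | Cut, placebo / valacyclovir | Person-years removed, placebo / valacyclovir | Total (share of 1,170) | Year-1 window, valacyclovir ÷ placebo |
|---|---|---|---|---|
| 25% | 29.2 / 20.8 | 15.5 / 10.8 | 26.3 (2.2%) | 379.2/374.5 = 1.013 |
| 50% | 58.5 / 41.5 | 31.0 / 21.6 | 52.6 (4.5%) | 368.4/359.0 = 1.026 |
| 75% | 87.8 / 62.3 | 46.5 / 32.4 | 78.9 (6.7%) | 357.6/343.5 = 1.041 |
| 100% | 117.0 / 83.1 | 62.0 / 43.2 | 105.2 (9.0%) | 346.8/328.0 = 1.057 |

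The placebo loss is 62.0/43.2 = 1.4 times the valacyclovir loss at any q.

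**Lower end.** If all 200 endpoint participants took one two-week course and resumed, the time in no stated analysis is 200 × 2/52 = 7.7 person-years, or 0.7% of 1,170.

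**Months 12-18.** These are 780 × 0.5 = 390 person-years (33%). If the cut-off is month 18 instead, each participant cut without resumption also loses the last half-year: 26 + 0.25 × 200 × 0.5 = 51 person-years at q = 25%, and 105 + 200 × 0.5 = 205 at q = 100% (4-18% of 1,170). The gap exists under either reading.

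Herpes simplex treatment is also a trigger, but the documents give no rate for it, so it is not counted.

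**The case against.** The strongest reply is that the rule is deliberate. Someone on open-label valacyclovir is off study drug, and charging that drug's toxicity to placebo would blur the drug effect. This is a good reason to keep the on-treatment analysis. It is not a reason to have no other.

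The protocol also defers details to the SAP, including the kidney-failure monitoring rule. How that rule counts cases cannot be judged here. But section 10.3 states the cut-off itself: an SAP that follows it inherits the gap, and one that departs from it needs reconciling.

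There is partial cover elsewhere. Stroke, temporal arteritis, myocardial infarction and malignancy have rates by randomized arm as exploratory endpoints (4.2.3), and the DSMC reviews all reported SAEs (8.4.2). Neither is a by-arm comparison of all SAEs or of kidney failure.

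Several stronger readings are tempting but unsupported:
- A reader might infer that safety analysis stops whenever study drug stops. Section 10.3 lists only the end-of-study cut-off and receipt of antivirals.
- A reader might infer that the efficacy endpoint itself closes the window. The trigger is antiviral treatment, which is at the investigator's discretion. Under 6.1.8 study drug continues if only topical antivirals are prescribed.
- Adding months 12-18 to the antiviral cut gives 416-495 person-years outside the main window (36-42%). Of these, 390 rest on an ambiguous phrase and have nothing to do with outcome.
- A reader might infer a material tilt against valacyclovir from its longer window. The year-1 difference is about 1-6%, and the protocol does not say that crude proportions will be compared.

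**Conclusion.** The point holds in a limited form. The protocol states only on-treatment safety windows. SAEs and dialysis-requiring kidney failure during an open-label antiviral course, or after prolonged open-label use without resumption, have no stated by-arm comparison although they are recorded. Months 12-18 share that gap only if the cut-off is month 12.

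The size of the outcome-linked part depends on uptake and resumption, neither of which the documents give. It ranges from under 1% of follow-up (two-week courses, all resumed) to 2-9% (25-100% uptake, none resumed), under constant hazards and the plan's own event rates. The harm lies in omitted events and in follow-up that does not match the efficacy analysis. It is not evidence of a large bias between the arms.

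**What to change.** In sections 10.3 and 10.4.5, add a by-arm comparison of all SAEs and of dialysis-requiring kidney failure in every participant who took at least one dose, over 0-12 and 0-18 months from randomization, regardless of discontinuation or open-label antivirals. Keep the on-treatment analysis beside it and report it per person-year, since its window can differ by arm. State whether the end-of-study cut-off means month 12 or month 18, and make the SAP agree.

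The cost is some wording and a few tables from data already collected; sample size, visits and treatment do not change. The downside is that the all-follow-up comparison includes off-drug and open-label time and can dilute a pure drug effect, which the retained on-treatment analysis addresses.
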